9.2 GVHD prophylaxis

Ixazomib beginning between day +100 to +150 at a dose of 4 mg orally once per week (3 weeks on/ 1 week off). The patients will continue on this same dose until taper off from immunosuppressants or 1 year post-HSCT is reached (whichever occurs first) or until the patient develops GVHD or malignant disease relapse/progression occurs. Patients who reach 1 year post-HSCT or discontinue immunosuppressants mid-cycle should complete their current cycle of ixazomib.

- The levels of the drug will not be monitored while the patients are on study.
- In order for patients to receive drug, they must have a platelet count > 75K, Hgb (untransfused) > 8 and an ANC > 1.0 (can be supported with G-CSF)
- If more than 2 doses in a row or more than 3 doses total are held, the patient is removed from study.
- Doses are given weekly +/- 3 days

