9.1.1 Dose-modification guidelines

Treatment with ixazomib will use a cycle length of 28 days. For a new cycle of treatment to begin, the patient must meet the following criteria:

- ANC \geq 1,000/mm³
- Platelet count \geq 75,000/mm³
- Serum creatinine \leq 2.5 mg/dL and less than double from pre-treatment evaluation value

If the patient fails to meet the above-cited criteria for initiation of the next cycle of treatment, dosing should be delayed for 1 week. At the end of that time, the patient should be re-evaluated to determine whether the criteria have been met. If the patient continues to fail to meet the above-cited criteria, delay therapy and continue to re evaluate. The maximum delay before treatment should be discontinued will be 4 weeks or at the discretion of the Principal Investigator.

Ixazomib dose adjustments:

Dose Level	Dose (mg)
Starting Dose	4.0 mg
-1	3.0 mg
-2	2.3 mg

Table 9.1.1 Ixazomib dose adjustments for hematologic toxicities

Criteria	Action
Within-Cycle Dose Modifications	

 If platelet count $\leq 30 \times 10^9/L$ or ANC $\leq 0.50 \times 10^9/L$ on ixazomib dosing day (other than Day 1) If serum creatinine $> 2.5 \text{ mg/dL}$ or has doubled from pre-treatment evaluation 	
 Ixazomib dose should be withheld. Complete blood count (CBC) with differential should be repeated until the ANC and/or platelet counts have exceeded the prespecified values. Upon recovery, ixazomib may be reinitiated with 1 dose level reduction.
Dose Modifications for Subsequent Treatment Cycles	

 Delay of > 2 weeks in the start of a subsequent cycle due to lack of toxicity recovery as defined in Section 9.1.1 ANC $< 1.0 \times 10^9/L$, platelet count $< 75 \times 10^9/L$, serum creatinine $> 2.5 \text{ mg/dL}$, serum creatinine doubled from pre-treatment evaluation, or other nonhematologic toxicities $>$ Grade 1 or not to the patient's baseline condition 	
 Hold ixazomib until resolution as per criteria Section 9.1.1 Upon recovery, reduce ixazomib 1 dose level. The maximum delay before treatment should be discontinued will be 3 weeks or at the discretion of the PI.
Dose Modifications for Subsequent Treatment Cycles	

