		Grade 4: Life-threatening consequences; urgent intervention indicated
Grade 2 Rash	
• Symptomatic recommendations. The investigator and project clinician may discuss considerations for dose modifications and symptom management.	Grade 2: Rash covering 10-30% BSA with or without symptoms; limiting instrumental ADL
Grade \geq 3 nonhematologic toxicity judged to be related to study drug	
• Hold study drug until resolution to Grade \leq 1 or baseline• Reduce study drug to next lower dose upon recovery	
If not recovered to Grade \leq 1 or baseline within 4 weeks	
• Discontinue treatment	

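### The maximum delay of a cycle start is 4 weeks in the Section 9.1.1 text but 3 weeks in Table 9.1.1, and the blood counts required for mid-cycle doses are not stated consistently

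*Combined protocol and SAP*

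**What the plan says.** **Delay of a cycle start.** Section 9.1.1 lists the values a patient must meet before a new cycle ("For a new cycle of treatment to begin, the patient must meet the following criteria"). If they are not met, dosing is put back by a week at a time, and the text closes with: "The maximum delay before treatment should be discontinued will be 4 weeks or at the discretion of the Principal Investigator". Table 9.1.1 has a row for a late start of a later cycle. It refers back to the Section 9.1.1 criteria and ends: "The maximum delay before treatment should be discontinued will be 3 weeks or at the discretion of the PI".

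**Counts required for dosing.** Section 9.2 (GVHD prophylaxis) states: "In order for patients to receive drug, they must have a platelet count > 75K", and adds "Hgb (untransfused) > 8 and an ANC > 1.0". The within-cycle row of Table 9.1.1 withholds drug at platelets of 30 x10^9/L or less or ANC of 0.50 x10^9/L or less, and applies "on ixazomib dosing day (other than Day 1").

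**Held doses.** Section 9.2 (GVHD prophylaxis) takes a patient off study once the held doses exceed two consecutively or three in total. It does not define a held dose.

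The number 9.2 is used twice in the protocol. Here it always means the section titled GVHD prophylaxis, not the one titled Management of clinical events.

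**The concern.** These are safety rules for dosing patients with low counts or unresolved toxicity. If two sentences give different limits for one event, staff who follow the protocol faithfully can make different decisions for the same patient: one stops treatment, another resumes it at a reduced dose. If the counts needed for a mid-cycle dose depend on an unstated scope, one reader withholds a dose that another gives. A deviation cannot be judged consistently when the rule has two values.

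**Working it through.** No statistical calculation applies. The check sets the sections side by side, with a simple count of doses for the third item.

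**1. Maximum delay**

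| | Section 9.1.1 text | Table 9.1.1, late-cycle row |
|---|---|---|
| Event | New cycle cannot begin | Later cycle starts late |
| ANC | at least 1,000/mm³ to start (= 1.0 x10^9/L) | below 1.0 x10^9/L |
| Platelets | at least 75,000/mm³ to start (= 75 x10^9/L) | below 75 x10^9/L |
| Creatinine | at most 2.5 mg/dL and less than doubled to start | above 2.5 mg/dL or doubled |
| Default maximum delay | 4 weeks | 3 weeks |
| Investigator discretion | yes | yes |

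After unit conversion, the table's count and creatinine thresholds are the complement of those in the text. Both describe the same event. The difference is 4 − 3 = 1 week, and it affects a patient who recovers after week 3 and by week 4.

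**2. Counts for a mid-cycle dose**

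Inputs: Section 9.2 requires platelets > 75 and ANC > 1.0 (its ANC unit is not printed; x10^9/L is assumed, to match Section 9.1.1). Table 9.1.1 withholds a dose after Day 1 at platelets ≤ 30 or ANC ≤ 0.50.

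Take a dose after Day 1 with the creatinine trigger not met. Section 9.2 as worded bars the dose while the table's trigger does not withhold it when:
- platelets are above 30 and ANC is above 0.50, and
- platelets are at most 75 or ANC is at most 1.0.

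The table does not order a dose in this band; it simply does not withhold one.

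Evidence on the scope of the Section 9.2 line points both ways:
- For cycle start only: its values nearly match the new-cycle list in 9.1.1. Section 10.0 requires counts before doses 1 and 3 of cycles 1 and 2 and then only before dose 1, so no count is mandated before dose 2 in any cycle.
- For every dose: the line refers to receiving drug, without qualification. Section 9.1.2 also ties its platelet-transfusion restriction to every day of dosing.

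Even on the cycle-start reading the two lists are not the same. Section 9.2 has hemoglobin and no creatinine, and uses strict inequalities. Section 9.1.1 has creatinine and no hemoglobin, and includes the boundary values. They can be applied together, but the protocol does not say so.

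**3. Held doses (clarification only)**

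Doses fall on days 1, 8 and 15 of a 28-day cycle, with day 22 in the rest week. If a delayed start counts as holding the doses that were due:
- 1-week delay: day 1, so 1 dose
- 2-week delay: days 1 and 8, so 2 doses
- 3-week delay: days 1, 8 and 15, so 3 doses, and 3 > 2 means removal
- 4-week delay: days 1, 8 and 15, so 3 doses, and again removal

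If a delayed start only moves the calendar, the count is 0 and nothing conflicts. The protocol supports neither reading clearly: the 9.1.1 text speaks of delaying, while the table's action for the same event is to hold.

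**The case against.** The strongest reply is that both delay limits are defaults open to the principal investigator's discretion, so neither is a hard stop. That is true and softens the conflict, but it does not say which default applies before discretion is used.

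On the counts, the reply is that Table 9.1.1 plainly governs hematologic toxicity. Section 9.2.4 refers to the protocol's dose-modification rules for neutropenia (citing the table) and for thrombocytopenia, and Section 11.2 sends hematologic toxicity to Section 9.1.1. The section numbering has also slipped, so the count line may have been meant as part of the parent section of 9.1.1. Together with the count schedule in Section 10.0, this makes a cycle-start reading plausible. It stands as a reason for lower confidence, but the limitation is nowhere stated.

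Three stronger readings are tempting, and the documents do not support them.
- *Table 11.2 contradicts the 3-week limit for non-hematologic toxicity.* The 3-week row does mention "or other nonhematologic toxicities", and Table 11.2 discontinues if there is no recovery to Grade 1 or less "or baseline within 4 weeks". But Table 11.2 limits the time for a toxicity to recover, not the delay of a cycle. If its clock runs from the hold, drug held from day 15 reaches 4 weeks at day 15 + 28 = 43, which is only 43 − 29 = 14 days after the next cycle was due. Both limits can then apply without contradiction. Calling them the same limit needs an assumption.
- *The held-dose rule defeats the delay limits.* This follows only if a delayed start counts as held. Any finer calculation of which delay, to the day, escapes removal would rest on a counting convention that no section provides.
- *The trial loses power.* Section 12.3 counts drug-related discontinuation without resumption as a treatment failure, so the limit applied could affect a patient's classification. The documents give no rate for such cases, and no loss of power can be derived.

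**Conclusion.** The 3-week and 4-week limits are an internal inconsistency: one event, two defaults, one week apart, and no other section resolves it. Confidence is high and no assumption is needed. The count line conflicts with Table 9.1.1 as worded for mid-cycle doses in the band shown above. Confidence is moderate, because the conflict disappears if the line applies only at cycle start, although the two start lists would still differ. The held-dose point is a request for clarification with low confidence, since it depends wholly on whether a delayed start counts as held. No frequency of affected patients and no effect on the primary endpoint is claimed.

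**What to change.** - Bring the Section 9.1.1 text and Table 9.1.1 to one maximum delay. Alternatively, state separate limits by type of toxicity, and say how they relate to the recovery limit in Table 11.2.
- State whether the count line in Section 9.2 (GVHD prophylaxis) applies to every dose or only at cycle start. Align it with the new-cycle list in 9.1.1, the within-cycle row of Table 9.1.1 and the blood-count schedule in Section 10.0.
- State whether a delayed cycle start counts as held doses.

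Which limit, threshold or removal rule to keep is the sponsor's clinical decision. The cost is amendment wording. The sample size does not change, and any change to the blood-count schedule depends on the rule the sponsor keeps.

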9.1.2. Excluded concomitant medications and procedures

The following medications and procedures are prohibited during the study.

Systemic treatment with any of the following metabolizing enzyme inhibitors is not permitted in this study. A DDI with a strong inhibitor would increase the ixazomib exposure and could lead to a higher probability of an AE:

- Strong inhibitors of CYP1A2: fluvoxamine, enoxacin, ciprofloxacin
- Strong inhibitors of CYP3A: clarithromycin, telithromycin, itraconazole, voriconazole, ketoconazole, nefazodone, and posaconazole.

Systemic treatment with any of the following metabolizing enzyme inducers should be avoided, unless there is no appropriate alternative medication for the patient's use (rationale: Unlike with inhibitors, if there were to be a DDI with an inducer, ixazomib exposure would be less; therefore, there would be a reduced chance of an AE. However, there may be less chance for an antitumor effect, but that is not an absolute reason to be taken off ixazomib):

- Strong CYP3A inducers: rifampin, rifapentine, rifabutin, carbamazepine, phenytoin, and phenobarbital.
- Exclude foods and dietary supplements include St. John's wort and Ginkgo biloba.

The following procedures are prohibited during the study:

- The addition of immunosuppressant(s) and/or GVHD prophylactic agents once enrolled in the study.
- Platelet transfusions to help patient meet eligibility platelet level criteria are not allowed within 3 days prior to study drug dosing for any dosing day.

9.1.3. Precautions and restrictions

Fluid deficit should be corrected before initiation of treatment and during treatment. Nonsteroidal anti-inflammatory drugs (NSAIDs) should be avoided with impaired renal function given reported NSAID-induced kidney injury in patients with decreased renal function.

9.2 Management of clinical events

Adverse drug reactions such as thrombocytopenia, diarrhea, fatigue, nausea, vomiting, and rash have been associated with ixazomib treatment. Management guidelines regarding these events are outlined below. Further details of management of ixazomib AEs are described in Section 9.1.1

9.2.1 Nausea and/or vomiting

Standard anti-emetics including 5-hydroxytryptamine 3 serotonin receptor antagonists are recommended for emesis if it occurs once treatment is initiated; prophylactic anti-emetics may also be considered at the physician's discretion. Dexamethasone should not be administered as an anti-emetic. Fluid deficit should be corrected before initiation of study drug and during treatment.

9.2.2 Diarrhea

Prophylactic antidiarrheals will not be used in this protocol. However, diarrhea should be managed according to clinical practice, including the administration of antidiarrheals once infectious causes are excluded. If GVHD is suspect, proper evaluation including endoscopic evaluation with biopsy should be conducted. Fluid intake should be maintained to avoid dehydration. Fluid deficit should be corrected before initiation of treatment and during treatment.

9.2.3 Erythematous rash with or without pruritus

As with bortezomib, rash with or without pruritus has been reported with ixazomib, primarily at the higher doses tested and when given with agents where rash is an overlapping toxicity. The rash may range from limited erythematous areas, macular and/or small papular bumps that may or may not be pruritic over a few areas of the body, to a more generalized eruption that is predominately on the trunk or extremities. Rash has been most commonly characterized as maculopapular or macular. To date, when it does occur, rash is most commonly reported within the first 3 cycles of therapy. The rash is often transient, self-limiting, and is typically Grade 1 to 2 in severity.

Symptomatic measures such as antihistamines or corticosteroids (oral or topical) have been successfully used to manage rash and have been used prophylactically in subsequent cycles. The use of a topical, IV, or oral steroid (e.g., prednisone \leq 10 mg per day or equivalent) is permitted. Management of a Grade 3 rash may require intravenous antihistamines or corticosteroids. Administration of ixazomib (and/or other causative agent if given in combination) should be modified per protocol and re-initiated at a reduced level from where rash was noted.

In line with clinical practice, dermatology consult and biopsy of Grade 3 or higher rash or any SAE involving rash is recommended. Prophylactic measures should also be considered if a patient has previously developed a rash (e.g. using a thick, alcohol-free emollient cream on dry areas of the body or oral or topical antihistamines). A rare risk is Stevens -Johnson Syndrome, a severe and potentially life-threatening rash with skin peeling and mouth sores, which should be managed symptomatically according to standard medical practice. Punch biopsies for histopathological analysis are encouraged at the discretion of the investigator.

9.2.4 Neutropenia and thrombocytopenia

Blood counts should be monitored regularly as outlined in the protocol with additional testing obtained according to standard clinical practice. Growth factor support is not required but may be considered according to standard clinical practice. Ixazomib administration should be modified as noted as per dose modification recommendations in the protocol when neutropenia occurs (see Table 9.1.1). Therapy can be reinitiated at a reduced level upon recovery of neutropenia.

Thrombocytopenia may be severe but has been manageable with platelet transfusions according to standard clinical practice. Ixazomib administration should be modified as noted as per dose modification recommendations in the protocol when thrombocytopenia occurs. Therapy can be reinitiated at a reduced level upon recovery of platelet counts. A rare risk is thrombotic thrombocytopenic purpura (TTP), a rare blood disorder where blood clots form in small blood vessels throughout the body characterized by thrombocytopenia, petechiae, fever, or possibly more serious signs and symptoms. TTP should be managed symptomatically according to standard medical practice.

9.2.5 Fluid deficit

Dehydration should be avoided since ixazomib may cause vomiting, diarrhea, and dehydration. Acute renal failure has been reported in patients treated with ixazomib, commonly in the setting of the previously noted gastrointestinal toxicities and dehydration.

Fluid deficit should be corrected before initiation of study drug and as needed during treatment to avoid dehydration.

9.2.6 Hypotension

Symptomatic hypotension and orthostatic hypotension with or without syncope have been reported with ixazomib. Blood pressure should be closely monitored while the patient is on study treatment and fluid deficit should be corrected as needed, especially in the setting of concomitant symptoms such as nausea, vomiting, diarrhea, or anorexia. Patients taking medications and/or diuretics to manage their blood pressure, should be managed according to standard clinical practice, including considerations for dose adjustment of their concomitant medications during the course of the trial. Fluid deficit should be corrected before initiation of study as needed during treatment to avoid dehydration.

9.2.7 Posterior reversible encephalopathy syndrome

One case of posterior reversible encephalopathy syndrome, which ultimately resolved, has been reported with ixazomib. This condition is characterized by headache, seizures and visual loss, as well as abrupt increase in blood pressure. Diagnosis may be confirmed by magnetic resonance imaging (MRI). If the syndrome is diagnosed or suspected, symptom-directed treatment should be maintained until the condition is reversed by control of hypertension or other instigating factors.

9.2.8 Transverse myelitis

Transverse myelitis has also been reported with ixazomib. It is not known if ixazomib causes transverse myelitis; however, because it happened to a patient receiving ixazomib, the possibility that this drug may have contributed to transverse myelitis cannot be excluded.

10.0 EVALUATION DURING TREATMENT/INTERVENTION

All patients will be closely monitored and evaluated as per MSKCC BMT standard of care guidelines. Study specific assessment schedule listed in table below.

Evaluation includes history and physical examination, blood count, chemistry including liver function test at screening, 6 months and 12 months post-allograft. Blood counts and blood chemistries will be monitored before the initiation of each treatment cycle and prior to the third dose of cycles 1 and 2.

Toxicity assessment will be performed monthly during the duration of treatment or discontinuation of the study drug. Prior to initiating the first two cycles, toxicity assessments will be performed at MSKCC's main campus when feasible. Toxicity assessments for subsequent cycles can be collected via phone call.

Acute and chronic GVHD will be diagnosed and graded according to established criteria^{5,25}. Assessments will be obtained at approximately at day 100, 6 months, and 12 months. Additional time points will be done if clinically indicated.

Scheduled Study Assessments:

Procedures	Study time-points					
	Consent	Pre-Treatment Evaluation	Ixazomib Cycles 1-9	6 months post-HSCT	12 months post-HSCT	Safety Follow Up
Window	100 – 150 days post-HSCT	- 30 days prior to Dose 1	+/- 3 days	+/- 14 days	+/- 30 days	30 days after last treatment +/ - 7 days
Informed consent	X					
History/ Physical		X		X	X	
Karnofsky score		X				
CBC ¹		X	X			
Blood Chemistry/ CMP ¹		X	X	X	X	
Thyroid function test ²		X		X	X	
EKG		X				
Pregnancy test (if applicable)		X				
Urinalysis		X				
Immune function testing ³		X		X	X	
GVHD evaluation	X			X	X	
Toxicity assessment ⁴		X	X	X	X	X

¹ CBC and Chemistry are required prior to dose 1 and dose 3 for the first 2 cycles and then prior to first dose of each subsequent drug cycle

² Thyroid function test should include thyroid stimulating hormone (TSH) and free T4

³ Immune function testing is performed per institutional practice and is recommended at indicated study time points.

⁴ To be collected prior to first dose of each cycle.

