12.3 Criteria for treatment failure for the primary endpoint

- Study drug is discontinued and unable to resume due to drug related toxicity.
- New onset or recurrence of grade II-IV aGVHD (including GVHD flares).
- New onset of chronic GVHD.
- Administration of systemic therapy for treatment of GVHD.
- Development of secondary graft failure during the administration of the study drug.
- Mortality (transplant or treatment-related)

If treatment failure criteria is met, the patient will be removed from the study. A 30-day follow-up will be conducted for end-of-treatment evaluation for toxicity assessment. This follow-up may be conducted via phone call or in-person by the clinical team.

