17.3 Serious Adverse Event (SAE) Reporting

An adverse event is considered serious if it results in ANY of the following outcomes:

- Death
- A life-threatening adverse event
- An adverse event that results in inpatient hospitalization or prolongation of existing hospitalization
- A persistent or significant incapacity or substantial disruption of the ability to conduct normal life functions
- A congenital anomaly/birth defect

- Important Medical Events (IME) that may not result in death, be life threatening, or require hospitalization may be considered serious when, based upon medical judgment, they may jeopardize the patient or subject and may require medical or surgical intervention to prevent one of the outcomes listed in this definition

Note: Hospital admission for a planned procedure/disease treatment is not considered an SAE.

SAE reporting is required as soon as the participant signs consent and is registered. SAE reporting is required for 30-days after the participant's last investigational treatment or intervention. Any events that occur after the 30-day period and that are at least possibly related to protocol treatment must be reported.

An SAE must be reported to the IRB/PB within 5 calendar days of the event. The IRB/PB requires a Clinical Research Database (CRDB) SAE report be submitted electronically to the SAE Office as follows:.

For IND/IDE trials: Reports that include a Grade 5 SAE should be sent to [contact]. All other reports should be sent to [contact].

For all other trials: Reports that include a Grade 5 SAE should be sent to [contact]. All other reports should be sent to [contact].

The report should contain the following information:

Fields populated from CRDB:

- Subject's name (generate the report with only initials if it will be sent outside of MSK)
- Medical record number
- Disease/histology (if applicable)
- Protocol number and title

Data needing to be entered:

- The date the adverse event occurred
- The adverse event
- The grade of the event
- Relationship of the adverse event to the treatment (drug, device, or intervention)
- If the AE was expected
- The severity of the AE
- The intervention
- Detailed text that includes the following
 - A explanation of how the AE was handled
 - A description of the subject's condition
 - Indication if the subject remains on the study
 - If an amendment will need to be made to the protocol and/or consent form.

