The PI's signature and the date it was signed are required on the completed report.

For IND/IDE protocols:

The CRDB AE report should be completed as above. If appropriate, the report will be forwarded to the FDA by the SAE staff through the IND Office. Potentially serious toxicities are an expected part of transplant therapy. Adverse events (AEs) and serious adverse events (SAEs) will be captured and reported as outlined in the Departmental Standard Working Procedure titled "Adult Bone Marrow Transplant (BMT) Adverse Event (AE) and Serious Adverse Event (SAE) Guide". In addition, the expected adverse events outlined in Table 11.2 will be captured.

17.2.1

AEs which are serious must be reported to Takeda Pharmaceuticals/ Millennium Pharmacovigilance (or designee) from the first dose of study drug through 30 days after administration of the last dose of ixazomib. Any SAE that occurs at any time after completion of ixazomib treatment or after the designated follow-up period that the sponsor-investigator and/or sub-investigator considers to be related to any study drug must be reported to Takeda Pharmaceuticals/ Millennium Pharmacovigilance (or designee). In addition, new primary malignancies that occur during the follow-up periods must be reported, regardless of causality to study regimen, for a minimum of three years after the last dose of the investigational product, starting from the first dose of study drug. All new cases of primary malignancy must be reported to Takeda Pharmaceuticals/ Millennium Pharmacovigilance (or designee).

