17.3.3 Procedures for Reporting Serious Adverse Events

AEs may be spontaneously reported by the patient and/or in response to an open question from study personnel or revealed by observation, physical examination, or other diagnostic procedures. Any clinically relevant deterioration in laboratory assessments or other clinical finding is considered an AE. When possible, signs and symptoms indicating a common underlying pathology should be noted as one comprehensive event. For serious AEs, the investigator must determine both the intensity of the event and the relationship of the event to study drug administration. For serious pretreatment events, the investigator must determine both the intensity of the event and the relationship of the event to study procedures.

Planned hospital admissions or surgical procedures for an illness or disease that existed before the patient was enrolled in the trial are not to be considered AEs unless the condition deteriorated in an unexpected manner during the trial (e.g., surgery was performed earlier or later than planned). All SAEs should be monitored until they are resolved or are clearly determined to be due to a patient's stable or chronic condition or intercurrent illness(es).

Since this is an investigator-initiated study, the principal investigator ([name]), also referred to as the sponsor-investigator, is responsible for reporting serious adverse events (SAEs) to any regulatory agency and to the sponsor- investigator's EC or IRB.

Regardless of expectedness or causality, all SAEs (including serious pretreatment events) must also be reported in English to Takeda Pharmaceuticals/ Millennium Pharmacovigilance (or designee):

Fatal and Life Threatening SAEs within 24 hours but no later than 5 calendar days of the sponsor-investigator's observation or awareness of the event.

All other serious (non-fatal/non life threatening) events within 5 calendar days of the sponsor-investigator's observation or awareness of the event

See below for contact information for the reporting of SAEs to Takeda Pharmaceuticals/ Millennium Pharmacovigilance.

The sponsor-investigator must fax or email the de-identified SAE Form per the timelines above. A sample of an SAE Form will be provided.

The SAE report must include at minimum:

- **Event term(s)**
- **Serious criteria**

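### The safety contact may precede the end of the 30-day SAE window by up to 7 days, and the protocol gives two different starts for SAE reporting to the manufacturer

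*Combined protocol and SAP*

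**What the plan says.** **End of the window.** The schedule in Section 10.0 sets the Safety Follow Up column, which carries a toxicity assessment, at "30 days after last treatment +/ - 7 days". Section 12.3 says of patients who meet a failure criterion that they leave the study and that "A 30-day follow-up will be conducted for end-of-treatment evaluation for toxicity assessment", by phone or in person. On reporting to the IRB/PB, Section 17.3 states that "SAE reporting is required for 30-days after" the participant's final study treatment; later events must still be reported if at least possibly related. For the manufacturer, the paragraph numbered 17.2.1 (placed within Section 17.3) sets the period as "from the first dose of study drug through 30 days after administration of the last dose of ixazomib".

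**Start of the window.** For the IRB/PB, Section 17.3 says "SAE reporting is required as soon as the participant signs consent and is registered". For the manufacturer, paragraph 17.2.1 starts at the first dose, as just quoted. Section 17.3.3, on the same recipient, says "Regardless of expectedness or causality, all SAEs (including serious pretreatment events) must also be reported in English". It also asks the investigator to judge the intensity of serious pretreatment events and their relation to study procedures.

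**Time limit.** Section 17.3.3 asks for "Fatal and Life Threatening SAEs within 24 hours but no later than 5 calendar days" of awareness, and for all other SAEs within 5 calendar days.

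**The concern.** Adverse events and SAEs are the trial's stated safety endpoint, and Section 14.0 promises a tabulation of their frequency and severity. That tabulation is only as complete as the ascertainment behind it. If the last scheduled safety contact can fall before the reporting window closes, a follow-up done exactly to protocol may not ask about the final days of the window. Within those days every SAE is reportable whatever its cause; the restriction to possibly related events applies only afterwards.

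At the other end, staff who receive a report of an SAE after consent and registration but before the first dose find one instruction that leaves it out of manufacturer reporting and another that requires it. For fatal and life-threatening events, the outer limit is the same as for any other SAE, so it is unclear whether the 24-hour limit binds.

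**Working it through.** No sample size, power or error rate is involved. The check is day arithmetic and a comparison of sections.

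**1. Safety contact against the end of the SAE window**

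Inputs: target day 30 and tolerance 7 days (Section 10.0 schedule); SAEs reportable through day 30 after the last treatment or dose (Section 17.3 and paragraph 17.2.1).

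- Earliest compliant contact: 30 − 7 = day 23.
- Latest compliant contact: 30 + 7 = day 37.
- Reportable days left after a contact on day *d*: max(0, 30 − *d*).
- At *d* = 23: 30 − 23 = 7 days, namely days 24 to 30.
- At *d* = 30 to 37: 0 days.

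The gap is therefore 0 to 7 days, depending on when the contact is made. The documents do not say how often it is made early, so no average can be given.

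Whether a later assessment fills the gap depends on the patient:

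- *Removed at treatment failure:* Section 12.3 states only the 30-day follow-up. To indicate the size of this group, Section 14.0 uses GVHD rates of 40% and 60%. With 46 patients, 0.40 × 46 = 18.4 and 0.60 × 46 = 27.6, so about 18 to 28 patients could leave by the GVHD route alone. This counts patients on that route, not patients with a gap.
- *Not removed, treatment stopped well before 1 year:* the 6- or 12-month toxicity assessment may fall later and pick up events by history.
- *Treated until 1 year:* the 12-month assessment (± 30 days) is centred near the end of treatment, so it may well come before the safety contact.

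**2. Start of SAE reporting**

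| Place | Recipient | SAE after consent and registration, before first dose |
|---|---|---|
| Section 17.3 | IRB/PB | Report |
| Paragraph 17.2.1 | Manufacturer | Outside the stated period |
| Section 17.3.3 | Manufacturer | Report, regardless of causality |

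The second and third rows concern the same recipient and give different answers for the same event. The first row concerns a different recipient and is not a further conflict. It shows that SAEs in this interval are already to be reported within the trial.

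Longest possible interval: consent falls on days 100 to 150 (Section 10.0 schedule) and the drug is started on days 100 to 150 (Section 9.1), so 150 − 100 = 50 days. This needs consent and registration on day 100 and a first dose on day 150. It is a ceiling, and nothing in the documents suggests that it is typical.

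**3. Time limits for fatal and life-threatening SAEs**

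The two limits are 24 hours (1 day) and 5 calendar days, a difference of 5 − 1 = 4 days. The outer limit equals the 5 days set for all other SAEs, a difference of 5 − 5 = 0.

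**The case against.** The strongest reply on the end of the window is that every section uses 30 days and that ± 7 days is an ordinary visit tolerance. It does not end the duty to report on day 23. This stands: a reader might infer that the window is contradicted at both ends, but the documents support a contradiction only at the start.

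A reader might also infer that 7 of 30 days (23%) go unobserved in each patient. The documents do not support that. Seven days is the worst case, and contacts on days 30 to 37 leave no gap. Section 17.3.3 expects AEs to come from spontaneous reports and examination as well as from direct questions, and Sections 9.1 and 10.0 place patients under the institution's transplant care guidelines. Some late events will be caught that way. What remains is that the protocol does not make routine care its method for finding SAEs through day 30, and after treatment failure it states no other contact.

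On the start, it can be said that paragraph 17.2.1 does not forbid earlier reporting, so following Section 17.3.3 satisfies both. That is a workable reading, but staff should not have to infer it. The 50 days should not be read as a gap in SAE reporting overall, since Section 17.3 covers the interval for the IRB/PB. Nor do the documents support a worry that sites will diverge: they describe one centre and one responsible sponsor-investigator.

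The 24-hour and 5-day wording can fairly be read as a target with an outer limit. It is unclear rather than contradictory.

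**Conclusion.** The point holds in three parts of unequal weight.

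1. **Coverage gap at the end; a cheap improvement.** Up to 7 days of the 30-day window can fall after the last scheduled safety contact. This assumes the earliest compliant contact and no later assessment, and it is clearest for patients removed at treatment failure.
2. **Contradiction at the start; wrong as written.** Paragraph 17.2.1 and Section 17.3.3 cannot both define what goes to the manufacturer before the first dose. The interval is at most 50 days in theory, and only reporting to the manufacturer is in conflict.
3. **Minor clarification.** The text should say which limit binds for fatal and life-threatening SAEs.

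The effect is on the completeness and consistency of safety reporting. Sample size, error rates and the primary endpoint are untouched.

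**What to change.** - **Section 10.0 schedule:** change the Safety Follow Up window to day 30 with a tolerance of + 7 days only (days 30 to 37), and make Section 12.3 match. The cost is a scheduling range of 7 days in place of 14, with no added visit or call.
- **Paragraph 17.2.1 and Section 17.3.3:** give one start for SAE reporting to the manufacturer in both places. Consent and registration, the start that Section 17.3 already uses for the IRB/PB, would serve. Both conditions should be named, because Section 15.2 treats registration as a step of its own. The cost is a wording change; SAEs in this interval are already reportable to the IRB/PB.
- **Section 17.3.3:** state whether 24 hours or 5 calendar days is the binding limit for fatal and life-threatening SAEs and, if the other is kept, label it as a target. This too is wording only.
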